5. ANALYSIS POPULATIONS

The following analysis populations are planned for this study

- Safety Population: The safety population includes all subjects who received at least one Relizorb exposure.
- Intent to Treat Population (ITT): The ITT population, includes all subjects who received at least one RELiZORB exposure. This population is the same as safety, and will be used for efficacy analyses.
- Per Protocol Population (PP): The per protocol population consists of all subjects who
 met the inclusion criteria, used RELiZORB as stated in the protocol and Instructions For
 Use (IFU) through at least Visit 3 (Day 30) and had not been the subject of any major
 protocol deviation(s).

Protocol: 0000498 Page 14 of 87

Final Version 3.0

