6. GENERAL ISSUES FOR STATISTICAL ANALYSIS

6.1 General Statistical Methodology

The primary population for safety is the safety population. For the efficacy analysis, the primary endpoint will be conducted on both the per protocol (PP) and ITT populations. All secondary efficacy analyses will be conducted on the ITT population unless otherwise specified.

Continuous variables will be summarized using descriptive statistics, including number of nonmissing values, mean, standard deviation, median, minimum, and maximum. Qualitative variables will be summarized using the number and proportion of each possible value.

The minimum and maximum will be reported with the same degree of precision (i.e., the same number of decimal places with a maximum of 1 decimal place) as the raw data. Measures of location (mean and median) will be reported to 1 degree of precision (with a maximum of 2 decimal places) more than the raw data and the measure of spread (standard deviation) will be reported to 2 degrees of precision (with a maximum of 3 decimal places) more than the raw data. All efficacy endpoints in section 8.1 will use a maximum of two decimal places.

Categorical (qualitative) variable summaries will include the frequency and percentage of subjects who are in the particular category. The denominator for the percentage calculation will be based upon the total number of subjects in the relevant study population unless otherwise specified.

Assessments done on unscheduled visits will not be summarized but will be listed. If any assessments are repeated on the same day and/or time point, the last non-missing assessment will be summarized and/or analyzed.

Statistical tests will be conducted at the 0.05 significance level using 2-tailed tests, and nominal p-values will be reported. SAS software (SAS, Inc., Cary, NC) will be utilized for statistical analysis (version 9.3).

Subject level information presented in a listing will include subject identification number as well gender, age (examples: F/23, M/37). All listings will be sorted by subject identification numbers.

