6.2 Handling of Missing Data

Available subject data will be used in the statistical analysis. For the MMRM analysis, subjects who lack all post-baseline measures, the baseline efficacy outcome will be imputed for all post-baseline responses (i.e., no change from baseline).

To handle missing or partial AE and medication dates, the following rules will be applied.

For partial start dates:

- 1. If the year is unknown, then do not impute the date but assign a missing value
- 2. If the month is unknown, then:
 - a. If the year matches the year of the first RELiZORB administration date, then impute the month and day of the first RELiZORB administration date.
 - b. Otherwise, assign "January."
- 3. If the day is unknown, then:

a. If the month and year match the month and year of the first RELiZORB administration date, then impute the day of the first RELiZORB administration date.

b. Otherwise, assign "01."

For partial end dates:

- 1. If the year is unknown, then do not impute the date but assign a missing value.
- 2. If the month is unknown, then assign "December."
- 3. If the day is unknown, then assign the last day of the month.

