8.1 Primary Efficacy Endpoint

Fatty acid erythrocyte tissue composition of the total of DHA plus EPA is the primary efficacy endpoint and is measured at visits 1 through 5 on days -14, 0, 30, 60, and 90, respectively. The primary efficacy endpoint (actual values) will be analyzed by a mixed model repeated measures (MMRM) model to test for LS Mean differences relative to baseline (as defined in Section 6.3) among the post-baseline visits. For this analysis, study visit 2 (day 0), 3 (day 30), 4 (day 60), 5 (day 90) is a categorical effect and subject is a random effect. The primary study population compares baseline to Day 90 in the ITT population. For subjects who lack visit 2, the value at visit 1 will be used.

An unstructured within-subject covariance matrix will be used. If the model does not converge, auto-correlated, and compound symmetry will be explored and the model resulting in the lowest Akaike information criterion value will be presented. LS Means, standard errors (SE), and 95% confidence intervals will be reported by visit. Contrasts in LS Means at each visit against baseline will also be reported with SE and 95% confidence intervals with p-values for differences from zero. A sensitivity analysis of the primary efficacy endpoint will be conducted in the PP population.

Summary statistics for actual values at each visit and changes from baseline will be presented.

The primary endpoint analysis will be repeated by age subgroups and by CFRD subgroups separately.

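### SAP 8.1 adds a random subject effect to an unstructured covariance, names no degrees-of-freedom method, and does not define the non-convergence that triggers its fallback

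*SAP*

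**What the plan says.** SAP 8.1 models actual values of erythrocyte DHA plus EPA at Days 0, 30, 60 and 90. It states that visit "is a categorical effect and subject is a random effect", and then: "An unstructured within-subject covariance matrix will be used. If the model does not converge, auto-correlated, and compound symmetry will be explored". Of the two alternatives, "the model resulting in the lowest Akaike information criterion value will be presented". SAP 10 also describes the model as having both random and fixed effects.

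On inference, SAP 8.1 says: "Contrasts in LS Means at each visit against baseline will also be reported with SE and 95% confidence intervals with p-values". The primary comparison is Day 90 against baseline in the ITT population. SAP 6.1 says: "Statistical tests will be conducted at the 0.05 significance level using 2-tailed tests, and nominal p-values will be reported". It names SAS 9.3, but no procedure and no degrees-of-freedom option.

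The model is reused widely. "The primary endpoint analysis will be repeated by age subgroups and by CFRD subgroups separately", and SAP 8.2 and 8.3 apply it to the secondary and the laboratory exploratory endpoints. Under SAP 5, "The ITT population, includes all subjects who received at least one RELiZORB exposure". SAP 6.2 adds that, for the MMRM, "subjects who lack all post-baseline measures, the baseline efficacy outcome will be imputed for all post-baseline responses".

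**The concern.** An unstructured matrix already describes every variance and covariance among the four visits. A random intercept adds one constant to every element of that matrix, which the unstructured part can absorb exactly. The data cannot separate the two.

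Three consequences follow.

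- **Trigger.** The redundant model has a singular Hessian. SAP 8.1 does not say whether that counts as a failure to converge. Two competent programmers could report different primary models from the same data.
- **Fallback.** Once triggered, it moves from 10 free parameters to structures with two. AIC compares only those structures with each other, so it cannot show that both are wrong.
- **Degrees of freedom.** None are specified, and the literal model permits a choice larger than the unstructured Day 90 contrast supports.

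At stake are the standard error, interval and p-value of the primary contrast, not its estimate when data are complete.

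**Working it through.** **The plan's own figure.** SAP 3.2 gives 80% power for 30 subjects at effect size 0.53. A paired t-test (noncentral t, 29 df, two-sided 0.05) gives 80.1%, so the figure reproduces. With complete data, the unstructured model's Day 90 contrast with n − 1 df is this same test.

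**Parameter count** (four visits, SAP 8.1; rank of the map from parameters to the 10 distinct elements of the marginal covariance):

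| Model | Parameters | Identifiable |
|---|---|---|
| Unstructured | 4 × 5 / 2 = 10 | 10 |
| Unstructured + random subject | 11 | 10 |
| Compound symmetry + random subject | 3 | 2 |
| AR(1) + random subject | 3 | 3 |

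If the random term is kept in the fallback, the redundancy therefore returns under compound symmetry.

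**Degrees of freedom.** With the random term coded, containment df = 4n − (n + 3) = 3(n − 1). The unstructured contrast carries n − 1. Actual type I error is P(|t with n − 1 df| > 97.5% point of t with 3(n − 1) df), exact for complete normal data:

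| n | Point, n − 1 df | Point, 3(n − 1) df | Interval width ratio | Type I error |
|---|---|---|---|---|
| 30 | 2.045 (29) | 1.988 (87) | 0.972 | 5.6% |
| 40 | 2.023 (39) | 1.980 (117) | 0.979 | 5.5% |
| 10 | 2.262 (9) | 2.052 (27) | 0.907 | 7.0% |
| 5 | 2.776 (4) | 2.179 (12) | 0.785 | 9.5% |

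**Why the fallback can err in either direction.** With complete data, compound symmetry estimates the variance of the Day 90 minus Day 0 difference as 2 × (mean visit variance − mean covariance). Two assumed examples:

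- All SDs 1, correlations with baseline 0.5, later correlations 0.8. Mean correlation = (3 × 0.5 + 3 × 0.8) / 6 = 0.65. Model: 2 × 0.35 = 0.70. Truth: 2 × 0.5 = 1.00. The standard error is √0.70 = 0.84 of its true value, too small.
- SDs 1, 1.5, 1.5, 1, all correlations 0.7. Mean variance = 6.5 / 4 = 1.625. Mean covariance = 0.7 × 9.25 / 6 = 1.079. Model: 2 × 0.546 = 1.092. Truth: 2 × 0.3 = 0.60. The standard error is √1.82 = 1.35 times its true value, too large.

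**Fallback as planned** (REML fits of compound symmetry and AR(1), lower AIC, 87 df, n = 30, complete data, no true change; simulated). Covariances are assumed, not taken from the documents:

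| Assumed pattern | Type I error, random term dropped | Type I error, random term kept |
|---|---|---|
| One of the two structures true | 4.7%–5.6% | 4.8%–6.6% |
| Equal SDs, lower baseline correlations | 7.0%–7.6% | 7.1%–8.0% |
| SD rising to 1.25–1.5 times or falling to 0.75 times | 3.3%–7.1% | 3.6%–7.2% |
| SD rising, then returning | 0.9%–3.0% | 0.8%–3.2% |
| Random-slope growth to 1.1–1.25 times | 6.1%–6.9% | 5.9%–7.8% |

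The unstructured model with 29 df gave 4.6%–5.3%. Dropout was not simulated, apart from a check of the SAP 6.2 imputation (n = 35, two subjects set to no change, three patterns): fallback 4.8%–6.9%, unstructured 4.8%–5.0%.

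**Small subgroups.** A 4 × 4 sample covariance is nonsingular only if n − 1 ≥ 4, so fewer than five subjects cannot support the unstructured matrix. SAP 6.3 sets a stratum of 19 years and over, and Protocol 4.1.1 expects mostly paediatric subjects while encouraging recruitment across ages. At assumed adult shares of 10%, 20% and 30%, the binomial chance of fewer than five adults is 82%, 26% and 3% with 30 subjects, and 63%, 8% and 0.3% with 40.

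**The case against.** In ordinary MMRM usage, subject often only names the cluster. On that reading the redundancy disappears, and an unstructured matrix alone should be estimable at n = 30. This stands, and it limits the importance. It leaves the degrees of freedom and the trigger undefined, and SAP 10 favours the literal reading.

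The degrees-of-freedom effect depends on the random term being coded and on containment being used. Neither document names containment. This also stands: the effect is conditional, and small for the main test.

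The subgroup analyses are supportive repeats with nominal p-values, and the adult shares are assumptions. Both are fair. Nominal p-values should still be computed with the right reference distribution.

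Stronger readings are tempting, and the documents do not support them:

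- A reader might infer that the primary result is biased. The redundancy changes neither the estimate nor its standard error at the maximum.
- A reader might infer a type I error near 11%, from compound symmetry fitted to autocorrelated data with correlation 0.7. That forces the wrong structure. SAP 8.1 selects by AIC, which chose the true structure in about 93%–99% of simulated trials when one of the two was true.
- Strong random-slope growth, with SD reaching 1.5 to 2 times baseline, gives up to 18.8%. Nothing in the documents suggests such growth.
- A reader might take equal variances as certain in the fallback. The autocorrelated structure is not defined; a heterogeneous version would restrict only the correlations.

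**Conclusion.** The point holds, at low to moderate importance. The literal model is over-parameterised by one (11 against 10), and the resulting singularity may itself set off a fallback whose trigger is undefined.

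If the random term is coded and containment degrees of freedom are used, Day 90 type I error is 5.6% instead of 5.0% at n = 30, with an interval 2.8% too narrow. In a subgroup of 10 it is 7.0%. These figures assume complete normal data.

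If the fallback is reached, type I error at n = 30 ranges from about 1% to 8% over the moderate patterns tried, assuming standard-form structures and 87 df. These are illustrations, not bounds. Neither the frequency of the fallback nor the direction of its error is established. The clearest case where the unstructured matrix must fail is a subgroup of fewer than five.

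**What to change.** In SAP 8.1:

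- Delete the clause that makes subject a random effect. Fit visit as the repeated factor within subject, with an unstructured covariance, REML and Kenward-Roger degrees of freedom.
- Define non-convergence: the convergence criterion is not met, or the Hessian or covariance matrix is not positive definite.
- Replace the AIC choice with an ordered fallback that allows unequal visit variances. Heterogeneous Toeplitz is one option. End with the paired t-test of Day 90 minus baseline.
- State that the no-change imputation in SAP 6.2 also applies to that t-test, so that the ITT set stays defined.
- For a subgroup of fewer than five, give summary statistics and at most the paired t-test.

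Apply the same rules to SAP 8.2, SAP 8.3 and the subgroup tables.

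The cost is SAP wording and a few lines of code. Intervals are slightly wider than with 87 df. In the final fallback step only, subjects with some post-baseline data but no Day 90 value are lost. This can happen because Protocol 4.1 asks evaluable subjects to complete only Day 60. Power at effect size 0.53 is then 80.1% with 30 subjects, 77.1% with 28 and 73.8% with 26.

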3.2 Sample Size

The proposed study with 30 complete and evaluable subjects would have 80% power to detect a minimum effect size of 0.53. Based on literature reviews using 1.5% as the maximum standard deviation expected when measuring DHA levels in plasma, the study should be able to detect an absolute increase of at least 0.8% from the baseline DHA value after 90 days of RELiZORB use (i.e., a change from 3.0% at baseline to 3.8% after 90 administration days or a 27% relative increase). This sample size will be adequate to detect the desired 30% relative increase in DHA levels.

The primary efficacy endpoint for this study is the sum of DHA+EPA. The sample size was based on a literature review of DHA assuming an effect size of 0.53. Assuming the same effect size for measuring erythrocyte tissue composition of the total of DHA plus EPA is consistent with that of DHA, the current sample size will provide 80% power.

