3.3 Subject Replacement

Approximately 30 to 40 subjects were to be enrolled in the study. Protocol compliant subjects from Protocol 0000497 were eligible for this study, unless clinical changes had occurred in which the patient no longer met the initial eligibility criteria.

Any subject who withdrew from the study before Study Visit 4 on Day 60 was to be replaced by an eligible subject unless enrollment was closed.

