8.3.1 Weight Gain Velocity

Weight gain velocity changes from historical average (baseline) to 0-90 days by age subgroup will be assessed by a one-sample t-test if the test for normality by Shapiro-Wilkes is met, or otherwise by the Wilcoxon signed rank test.

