8.3.2 Weight and BMI Z-scores

Age-specific z-scores for weight and BMI are obtained (via CDC standard tables) at each study visit and at quarterly intervals in the year prior to baseline. For weight and for BMI, the average historical distribution percentile (mean of historical values) and the z-scores (and distribution percentile) at 30, 60 and 90 days will be presented. The change in percentile of the distribution from historical average to 90 days will be tested by a one-sample t-test or Wilcoxon signed rank test. This analysis will be performed by age subgroup only.

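### Subgroup analyses are separate refits with no test of whether groups differ, and the SAP tests growth only within age groups although the protocol plans a whole-sample weight gain velocity comparison

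*SAP*

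**What the plan says.** **Fatty acids and vitamins.** SAP 8.1 fits an MMRM to four visits with an unstructured covariance and tests each post-baseline visit against baseline. It then says: "The primary endpoint analysis will be repeated by age subgroups and by CFRD subgroups separately". SAP 8.2 repeats three secondary endpoints by age and by CFRD status. SAP 8.3 repeats vitamins A, D and E by age. SAP 6.3 defines three age groups (12 and under, 13 to 18, 19 and over) and two CFRD groups.

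**Error rate.** SAP 6.1: "Statistical tests will be conducted at the 0.05 significance level using 2-tailed tests, and nominal p-values will be reported". Neither document contains a subgroup-by-visit term, a heterogeneity test or a pooled model with a subgroup effect. Protocol 7.1 says that the influence of covariates such as age will be looked at, but gives no method.

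**Growth.** SAP 8.3.1 tests "Weight gain velocity changes from historical average (baseline) to 0-90 days by age subgroup". SAP 8.3.2, on weight and BMI percentile change, says: "This analysis will be performed by age subgroup only". Tables 14.2.1.10 and 14.2.1.11 in SAP 12.1 are also titled by age subgroup. Protocol 7.8 compares historical with study weight gain velocity by a two-sided test, without an age split.

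**The concern.** A separate test against zero in each group does not address whether the groups differ. When each group has modest power, some will reach p<0.05 and others will not, even if the benefit is the same in all. A table showing significance in, say, adolescents but not adults invites a claim of differential benefit that no planned analysis can check.

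For growth, the subgroup analysis replaces the whole-sample analysis in the SAP instead of supplementing it. Growth is a stated efficacy objective in both documents, so an objective about all subjects would be answered only in fractions of the sample, by a change from the protocol that is not recorded.

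**Working it through.** **Inputs from the documents**
- Two-sided alpha of 0.05, nominal (SAP 6.1).
- Whole-study design: "The proposed study with 30 complete and evaluable subjects would have 80% power to detect a minimum effect size of 0.53" (SAP 3.2).
- Its components: "using 1.5% as the maximum standard deviation expected when measuring DHA levels in plasma" and an "absolute increase of at least 0.8% from the baseline DHA value", so 0.8/1.5 = 0.533.
- Enrolment: "Approximately 30 to 40 subjects were to be enrolled in the study" (SAP 3.3).

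**Assumptions**
- Subgroup sizes are not given. Even age groups of 10 or 12 correspond to 30 or 36 subjects. Protocol 4.1.1 expects mostly pediatric subjects, so uneven splits are tried too.
- The true effect is the same in every group.
- The MMRM contrast is approximated by a paired t-test.

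**Step 1: reproduce the plan's figure.** Power = P(|T| > t(0.975, n-1)), where T is noncentral t with n-1 df and noncentrality d√n. For n = 30 and d = 0.53, the noncentrality is 0.53 × 5.477 = 2.90 and power is 80.1%. The stated 80% is reproduced.

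**Step 2: the same formula at subgroup size.** Power is 32.3% at n = 10, 38.8% at n = 12 and 48.1% at n = 15. The effect detectable with 80% power is 1.00 SD at n = 10 and 0.89 SD at n = 12, against 0.53 SD for the whole study.

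**Step 3: chance that groups disagree on p<0.05.** With independent groups of power p_i, this is 1 - Πp_i - Π(1-p_i). For 12/12/12: 1 - 0.388³ - 0.612³ = 1 - 0.058 - 0.229 = 0.713.

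| Split | Power by group | All significant | None significant | Disagree |
|---|---|---|---|---|
| Age 10/10/10 | 32% each | 3% | 31% | 66% |
| Age 12/12/12 | 39% each | 6% | 23% | 71% |
| Age 15/10/5 | 48%, 32%, 15% | 2% | 30% | 68% |
| Age 20/10/5 | 61%, 32%, 15% | 3% | 22% | 75% |
| CFRD 15/15 | 48% each | 23% | 27% | 50% |
| CFRD 10/20 | 32%, 61% | 20% | 26% | 54% |
| CFRD 10/25 | 32%, 72% | 23% | 19% | 58% |

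**Step 4: sensitivity to the effect size.** For three age groups of 10 or 12, disagreement is 71% or 61% at d = 0.8, 47% or 31% at d = 1.0, and 4% or 1% at d = 1.5.

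**Step 5: a direct comparison of groups.** In 200,000 simulated trials (three groups of 10, uniform effect 0.53), a one-way F-test on change rejected in 5.0%, its nominal rate. Such a test has low power: with 15 against 15, the difference detectable with 80% power is about 1.06 SD.

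**Step 6: number of Day 90 subgroup tests.** Four endpoints × 5 groups = 20; three vitamins × 3 age groups = 9; velocity in 3 age groups = 3; weight and BMI in 3 age groups = 6. The total is 38, all at nominal 0.05.

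**Step 7: growth, side by side.** Protocol 7.8 has one unsplit velocity comparison; SAP 8.3.1 and Table 14.2.1.11 have it by age group. The one SAP section 10 entry for protocol 7.8 concerns ANOVA being replaced by MMRM. It does not mention the velocity comparison or an age split. No growth effect size is given. Purely as illustration, a standardised change of 0.53 would have 80% power in 30 subjects and 86% in 35, against 32% to 39% in groups of 10 to 12.

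**The case against.** The SAP never says that subgroups will be compared by their significance. It calls the p-values nominal, reports standard errors and 95% confidence intervals, and classes growth as exploratory. An interaction test in about 30 subjects would detect only very large differences, and a null result could be misread as homogeneity. All of this stands and lowers the severity. It does not supply a comparison between groups.

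On growth, SAP 4.2 says that final analyses identified in the protocol as well as the SAP will be performed, and section 10 does not withdraw the velocity comparison. The table shells are not in the text I had, so an overall column cannot be excluded. A reader might infer that growth has no overall test at all. The documents do not support that: protocol 7.8 plans one for velocity. What stands is an unreconciled difference between protocol and SAP.

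Other stronger readings also fail:
- A reader might infer that discordant results are virtually certain, since 1 - 0.388³ = 94%. That is the chance that at least one age group is non-significant, and it includes the 23% in which all three are and so agree.
- A reader might take 10 to 12 as the size of every subgroup. It is an even-split assumption for age only; two CFRD groups would average 15 or more.
- A reader might infer that the 10 covariance parameters make the subgroup fits unusable. With complete data the Day 90 contrast is essentially a paired t-test, and SAP 8.1 has fallback structures.
- A reader might expect tighter subgroup intervals from pooling. That requires equal variances from young children to adults, which neither document supports.

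**Conclusion.** The point holds as a low-severity improvement. At the design effect of 0.53 SD, shared by all groups, disagreement on p<0.05 is likely: about 66% to 75% across the age splits tried, and about 50% to 58% for CFRD. These figures rest on assumed subgroup sizes, independent groups, the paired-t approximation and the design effect itself, which SAP 3.2 gives as the minimum detectable rather than the expected effect. Disagreement becomes rare if the true effect is about three times as large.

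The growth point rests on the text alone: the SAP narrows a protocol comparison to age groups without listing or justifying the change. Its cost in power cannot be sized from the documents.

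**What to change.** 1. For each subgroup factor, fit one MMRM with visit, subgroup and visit-by-subgroup, allowing group-specific covariance if variances differ. Report the Day 90 contrast in each group and the between-group difference in change, all with 95% confidence intervals, plus the interaction p-value. State that the interaction test has low power and that subgroup p-values are descriptive.
2. Reconcile SAP 8.3.1 with protocol 7.8 by adding the whole-sample weight gain velocity test. In SAP 8.3.2, add an overall test of weight and BMI z-score or percentile change in subjects within the CDC 2 to 20 year reference (SAP 6.3.1.2). Keep the age-group results as supportive displays, and record any remaining departure in SAP section 10.

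The cost is some SAP wording and code. No new data are needed, and fewer models are fitted. With group-specific covariance, the within-group estimates will be close to those already planned; the gain is the direct comparison between groups. The main downside is that a non-significant interaction will say little, so the interval for the difference should carry the interpretation.
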